Exclusion Criteria: 1) Defined neurological or neurodegenerative disorder (e.g., history of head injury with loss of consciousness > 5 minutes, epilepsy, Alzheimer's disease); 2) other psychiatric conditions (e.g., schizophrenia, schizoaffective disorder, bipolar disorder); and 3) current drug or alcohol use disorder, except for nicotine and marijuana 4) adults unable to consent, pregnant women, prisoner; 5) Have contraindications to methohexitol and ketamine as described in the package inserts; 6) non-English speakers; 7) Patients that cannot tolerate Methohexitol and Ketamine.

5. Number of Subjects

26 subjects meeting the inclusion criteria will be recruited for this investigation. Our total sample size ($n = 26$) allows for a conservative 15% attrition rate leaving a final sample size of 22. This recruitment rate of 26 subjects per year will complete subject recruitment 1 year after study initiation. Sample size calculation is based on the 2004 Perera et al. paper examining ictal power between a threshold group and suprathreshold group (Cohen's $d = 1.19$) with variances of .24 and .25 respectively. Assuming a power of .8 and a two-sided alpha (.05), we will need 11 patients in each group to adequately power our analysis, which is in line with our recruitment projections.

6. Study Timelines

Individual subjects will have 4 points (T1-T4) in the study with the endpoint being their last treatment. ECT is done three times weekly and a typical series includes 8-12 treatments. This means that patients will be enrolled and participating in research for approximately one month. The study period will be one year long with an additional three months for analysis for a total of 15 months.

7. Study Endpoints

The primary endpoints include change in depression rating scale. Changes in depression rating will be compared with total ictal power and postictal suppression along with presence and power of infra-slow waves on dcEEG.

8. Research Setting

Patients will be recruited through the UNMH ECT consult service. All data collection will take place at the UNM Center for Psychiatric Research, or the ECT service at the University of New Mexico. All clinical assessments and neuropsychological testing will be conducted in an interview room or in a private patient room.

9. Resources Available

PROTOCOL TITLE:

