Neuropsychological Assessments: The Montreal Cognitive Assessment, a measure of global cognitive function that is sensitive to gross neurocognitive abnormalities, will be used for screening for preexisting cognitive impairment [20, 21]. The Dot Counting Test will measure effort. The Test of Premorbid Function estimates premorbid intellectual function [22] that will be used as a potential covariate in analyses. The Autobiographical Memory Test will assess free recall and retrieval patterns (specific versus general) of retrospective autobiographical memories [23-25]. The Hopkins Verbal Learning Test-Revised (HVLT-R) will measure learning strategies, free recall, and recognition memory [26]. The Delis Kaplan Executive Function System (DKEFS) Color-Word Interference and Verbal Fluency Test measures processing speed, sequencing and cognitive flexibility [27-31]. To minimize practice effects, we will use three different published versions of the HVLT-R at each time point [32]. Also, we will construct a reliable change index for all cognitive variables of interest [33]. Following published guidelines, we will compute the HVLT-R percent retention score, which will be our primary outcome measure [34]. The percent retention score is a useful measure of hippocampal dependent memory function that reduces the possibility of over-estimating memory function from immediate and delayed free recall scores [34]. The entire neuropsychological battery (completion time < 60 minutes) will be used to compute composite z-scores that represent global cognitive function at each time point for secondary analysis.

ECT: The treating anesthesiologist will determine the appropriate dose for this procedure. The anesthetic agents include methohexitol and ketamine, general anesthetics, and succinylcholine, a depolarizing neuromuscular blocker. Subjects will be randomized into methohexitol and ketamine arms prior to the first ECT treatment. Both induction agents are considered standard of care during ECT. The first ECT session will determine individual seizure thresholds to ensure subsequent treatments are delivered at supra-threshold intensities. Motor, electroencephalographic and heart rate parameters will be recorded for each treatment.

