Study Protocol: Subjects will receive their baseline depression and cognitive assessment 0 to 48 hours prior to the first ECT session (T1). One day after the sixth ECT treatment (T3), subjects will receive their second depression and cognitive assessment. Treatments will continue thrice weekly until clinical response, which

PROTOCOL TITLE:

typically occurs between six and twelve treatments. The final assessment will occur after their last ECT treatment in the series (T4) and will include depression and cognitive assessments. DcEEG data will be collected at T1-T4 using a non-invasive cap that covers the patient's head. Per standard of care, change of electrode placement will be assessed at the midpoint (T2) by the treating psychiatrist. If the patient is not responding to ECT they may be switched from RUL to bitemporal placement. This assessment will not be affected by the research protocol.

13. Data Analysis

See effect size calculation in question #5 for hypothesis 1.1. To the best of our knowledge, spreading depression has never been studied in ECT (aside from our preliminary findings). We will use the effect size for hypothesis 1.1 to guide us. In terms of analyzing the mean power of the waves noted, we plan to calculate the sum of the mean power per epoch across T1-T4 data points to get total ictal power, as well as smaller epochs to calculate total infra-wave power and post-infra-wave suppression. We will also use chisq to compare number of infra-slow waves and t-tests to compare power of infra-slow waves and total ictal power of seizures and post-ictal suppression in the methohexitol group. We do not expect to see infra-slow waves in the ketamine group.

14. Provisions to Monitor the Data to Ensure the Safety of Subjects

Methohexitol and ketamine are both standard of care anesthetic agents used in ECT and the dcEEG device is worn on the scalp and is non-invasive. If the patient does not tolerate the anesthetic chosen, then they will be switched to the other anesthetic and act as a cross-over cohort. The medications and ECT device used in this study are standard of care. In the unlikely event that at the midpoint assessment (6 months) greater than 50% of patients have refused to wear the EEG cap, our study will not be sufficiently powered and will be terminated.

15. Withdrawal of Subjects

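### The plan carries baseline cognition forward only through a reliable change index; any arm comparison of a cognitive outcome should model the follow-up score with that test's T1 score as covariate

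*Combined protocol and SAP*

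**What the plan says.** Section 12, Neuropsychological Assessments, states that "we will construct a reliable change index for all cognitive variables of interest". The citation for the index (reference 33) concerns its classical form. The following sentence reads "we will compute the HVLT-R percent retention score, which will be our primary outcome measure". The one covariate mentioned is the Test of Premorbid Function, which "estimates premorbid intellectual function [22] that will be used as a potential covariate in analyses". Composite z-scores are to be formed at each time point for secondary analysis, and no change scale is stated for them.

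Under Study Protocol in the same section, cognition is measured in the 48 hours before the first ECT (T1), one day after the sixth treatment (T3) and after the last treatment (T4).

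Section 13 names chi-square and t-tests for EEG measures. It gives no test, model or time point for a cognitive outcome.

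Elsewhere, Aim 1 and its three hypotheses name no cognitive test. Section 7 puts change in depression rating among the primary endpoints. Section 12, Clinical Assessments, makes change in the two QIDS versions the primary measure of clinical response.

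**The concern.** In its classical form a reliable change index is follow-up minus baseline, divided by a constant. A t-test on it is therefore the same as a t-test on the raw change. A change score subtracts the whole baseline value, which is the best use of the baseline only when the correlation between T1 and follow-up is close to 1. At lower correlations it carries baseline noise into the arm comparison, where a regression on T1 would remove it.

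With 22 patients expected in the analysis, precision is scarce. The T1 score is already to be collected, so better use of it costs nothing at the bedside. At stake is the width of the confidence interval for ketamine v methohexital on cognition, including the one cognitive measure that the plan calls primary.

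**Working it through.** **Inputs from the plan (Section 5).** The sample size rests on "ictal power between a threshold group and suprathreshold group (Cohen's $d = 1.19$) with variances of .24 and .25 respectively", with power 0.8 and two-sided alpha 0.05, and concludes that "we will need 11 patients in each group to adequately power our analysis". The 26 recruited "allows for a conservative 15% attrition rate leaving a final sample size of 22". These figures are for an EEG contrast, not for cognition.

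**The plan's own figure.** By the normal approximation, n per arm = 2(1.960 + 0.842)²/1.19² = 11.09, so 11 before rounding up. Power at 11 per arm is 79.7% by that approximation and 75.6% by the noncentral t. Attrition: 26 × 0.85 = 22.1. The stated 11 per group and 22 in all are reproduced.

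**Inputs assumed.** The documents give no cognitive effect size, SD or T1-to-follow-up correlation (rho). I take equal SDs at T1 and follow-up, normal scores, and rho from 0.3 to 0.9.

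**Variance, no effect size needed.** With SD = 1:
- change score: 2(1 − rho)
- follow-up adjusted for T1: 1 − rho²
- ratio, adjusted to change: (1 − rho²)/[2(1 − rho)] = (1 + rho)/2

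Before small-sample costs, a change-score analysis of 22 patients carries the information of 22 × 0.75 = 16.5 adjusted patients at rho 0.5, and 22 × 0.85 = 18.7 at rho 0.7.

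**Small-sample cost.** Adjustment leaves 22 − 3 = 19 residual degrees of freedom instead of 20. Estimating the slope also inflates the variance of the arm difference by an average factor of 1 + 1/18 = 19/18 at 11 per arm (chance T1 imbalance is chi-square on 1 df, divided by a within-arm sum of squares on 20 df whose reciprocal has mean 1/18). Break-even on variance is where (1 + rho)/2 × 19/18 = 1, so rho = 36/19 − 1 = 0.89.

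**Illustrative power.** Take d = 1.19 on the change-score SD, 11 per arm, two-sided 0.05. The change score has 75.6% power at every rho. For the adjusted analysis the effect size is 1.19 × √[2/(1 + rho)], which is 1.37 at rho 0.5 and 1.29 at rho 0.7. The fourth column uses 19 df but ignores slope estimation. The last column is from simulation and includes it.

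| rho | (1+rho)/2 | × 19/18 | Adjusted power, formula | Simulated gain over change score |
|---|---|---|---|---|
| 0.3 | 0.65 | 0.69 | 90.7% | about 13 points |
| 0.5 | 0.75 | 0.79 | 86.3% | 8 to 9 points (to about 84%) |
| 0.7 | 0.85 | 0.90 | 81.9% | about 4 points (to about 80%) |
| 0.8 | 0.90 | 0.95 | 79.7% | about 2 points |
| 0.9 | 0.95 | 1.00 | 77.5% | none |

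At d = 0.5 on the change-score SD the simulated gain is about 4 points at rho 0.5 and 2 at rho 0.7.

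**Where d is placed also matters.** If d = 1.19 is set on the follow-up SD instead, the formula difference between the two analyses is 18.0 points at rho 0.3, 10.7 at 0.5, 3.1 at 0.7 and 0.6 at 0.8.

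**The case against.** The strongest reply is that the plan never says the arms will be compared on the index. The sentence follows one on practice effects and fits a classification of individual patients. The measure called primary is percent retention, not its change index. Premorbid function is only a potential covariate, and nothing excludes T1. No hypothesis is cognitive, and this is a self-described pilot.

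Most of that stands. A reader might infer that the plan has chosen a change-score comparison and rejected T1 adjustment; the documents are silent on both, so the point has to be conditional. The silence still needs filling, because a measure labelled primary has no model, no time point and no stated use of its own baseline beyond the index.

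A reader might also infer that chance baseline imbalance biases the comparison. It does not. Over randomisation the change-score difference is unbiased. Given an observed T1 difference D, its expectation shifts by −(1 − rho)D, but that shift is part of the variance already counted above and is not a second harm.

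**Conclusion.** The point holds as a conditional one. If ketamine and methohexital are compared on the reliable change index, the result is valid but less precise than the T1 data allow whenever rho is below roughly 0.9 at this sample size. The variance saving is 25% at rho 0.5 and 15% at rho 0.7 before small-sample costs, and about 21% and 10% after the 19/18 factor. This rests on equal SDs and on assumed correlations.

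A fixed loss of power should not be attributed to this plan. Its d of 1.19 comes from ictal power in threshold v suprathreshold groups, and nothing in the documents links it to cognition or to the two anaesthetics. The power figures show how the gain depends on rho, d and the SD on which d is placed; they are not estimates for this trial. The direction of the advice is firm up to a rho of about 0.8. Its size is not known.

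**What to change.** In Section 12 or 13, state that any ketamine v methohexital comparison of a cognitive outcome is a linear model of the follow-up score on randomised agent, with that test's own T1 score as covariate. Report it as an adjusted difference with a 95% confidence interval at a named time point (T3 or T4). Keep the reliable change index as a per-patient descriptive summary. If power for cognition is quoted, give it with the assumed rho and effect size.

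Also reconcile the primary status of HVLT-R percent retention with the depression endpoints in Section 7 and under Clinical Assessments in Section 12, so that one hierarchy of outcomes is stated.

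The cost is a few sentences of analysis text and no new data or visits. The statistical price is one residual degree of freedom plus the cost of estimating the slope, with little or no gain if the correlation proves very high.

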been met with disappointing results [11]. EEG has also been evaluated as a potential biomarker in ECT, and there have been several advances that warrant a revisit to this line of inquiry. Firstly, traditional EEG filters out low frequency bands. Our preliminary data shows large infra-wave phenomena suggesting significant inhibitory activity (see figure 1) using dcEEG. This newly-captured neuronal activity during ECT could act by itself or in conjunction with ictal and postictal phenomena observed in normally observed frequency bands as a potential biomarker of treatment adequacy. Secondly, the EEG we propose is 24-lead, whereas prior investigations used up to 19-lead [12-14]. Our group has noticed more pronounced infra-slow waves in a subsection of the leads, meaning with greater resolution, we may be picking up neuronal activity that was previously missed. Thirdly, the studies evaluating EEG were carried out before ECT parameters were optimized with respect to seizure efficiency (high frequency and short pulse train duration). Current ECT devices have improved parameter ranges to individualize and optimize clinical outcomes.

3. Study Design

Figure 1: 24-Lead ECT capturing spreading depression (box with arrow)

PROTOCOL TITLE:

This single-site clinical investigation will use assessments before, during and after the ECT series. At the first time point (T1), subjects will be randomized to ketamine or methohexitol induction. The second time point (T2) will be the second ECT treatment. The third time point (T3) will occur midpoint, and the final time point (T4) will be the endpoint at the last ECT treatment. The patient will be blinded to the anesthetic.

4. Inclusion and Exclusion Criteria

Inclusion Criteria, Major Depressive Disorder (MDD) & Bipolar Disorder (BPD)-Depressed: 1) Structured Clinical Interview for DSM-5 will confirm diagnosis of MDD or BPD-depressed (with or without psychotic features); 2) the clinical indications for ECT including treatment resistance or a need for a rapid and definitive response; 3) Hamilton Depression Rating Scale 24-item (**HDRS-24**) ≥ 21 ; and 4) age range between 18 and 65 years of age. Per UNM ECT clinical service recommendations, subjects will be requested to taper and dc scheduled psychotropic medications with the exception of as needed medications for sleep or anxiety.

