If at any time a participant decides to withdraw from the study, the participant will be debriefed by the study coordinator or principal investigator as to the reason for their withdrawal. The participant will then be thanked for their time and compensated for the extent of their participation. If the participant wishes to withdraw, they will be asked if they will allow data already collected on them to be used in the study analysis. If not, the data associated to their identifying code will be purged from the study database.

16. Data Management/Confidentiality

Some mental health information will be retained, including primary diagnosis and results of scales/cognitive tests. Patient will be made aware at time of consent that data will be de-identified immediately and stored in a secure location, and that data used in final analysis will not have any identifiable markers and will be de-linked at close of study. Records will be kept strictly confidential and will not be inspected by any other agency unless required by law. Data will be de-identified as appropriate to the UNM Human Research and Review Committee and HIPPA requirements by assigning a randomized eight-digit number to each participant upon entry into the study. This number will be used for all correspondence between study investigators and all data collection and analysis after the initial screening visit. Any personal information entered into computers is password protected and monitored for suspicious activity. In order to contact subjects for telephone visits and/or other matters, it will be necessary to retain names and telephone numbers of active subjects. However, these direct identifiers will not be stored with any clinical data or subject information in order to protect confidentiality. Any direct identifiers will be stored in

PROTOCOL TITLE:

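### Total ictal power is a sum over T1-T4 with no rule for incomplete sets, so partial records from withdrawn patients can cost power for Hypothesis 1.1; Hypothesis 1.3 needs a sensitivity analysis for recordings after a placement change

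*Combined protocol and SAP*

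**What the plan says.** Section 13 (Data Analysis) defines the ictal-power outcome: "we plan to calculate the sum of the mean power per epoch across T1-T4 data points to get total ictal power". Totals are compared by t-test. The section gives no divisor, no minimum number of recordings and no rule for incomplete sets.

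Section 5 (Number of Subjects) recruits 26, which "allows for a conservative 15% attrition rate leaving a final sample size of 22", 11 per group at d = 1.19. Section 15 (Withdrawal of Subjects) says of participants who withdraw that "they will be asked if they will allow data already collected on them to be used in the study analysis".

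For Hypothesis 1.3, Section 7 (Study Endpoints) states: "Changes in depression rating will be compared with total ictal power and postictal suppression". Section 12 (Study Procedures) adds: "If the patient is not responding to ECT they may be switched from RUL to bitemporal placement". It places that review as follows: "change of electrode placement will be assessed at the midpoint (T2) by the treating psychiatrist". Section 3 (Study Design) makes T2 the second treatment and says: "The third time point (T3) will occur midpoint".

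**The concern.** A sum without a divisor measures two things at once: how strong the recorded seizures were, and how many were recorded. If partial records enter, the second becomes noise in the Hypothesis 1.1 comparison, the one on which the sample size rests. With 11 per arm there is little room for that noise. Keeping partial data could then be worse than discarding it.

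For Hypothesis 1.3 the issue is timing. A change of placement is triggered by non-response, and recording continues to T4. The sum set against depression change may therefore contain recordings made after, and because of, poor response.

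**Working it through.** **The plan's own figure.** Inputs from Section 5: d = 1.19, two-sided alpha 0.05, power 0.80.

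- n per group = 2(1.960 + 0.842)² / 1.19² = 11.09, in line with the stated 11 before rounding up.
- By the noncentral t, power is 0.756 with 11 per arm and 0.829 with 13 per arm.
- Attrition: 26 × 0.85 = 22.1, so 22 remain and 4 are lost, or 2 per arm if evenly split.

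**Complete sets.** With four recordings for everyone, sum = 4 × mean. The t statistic is unchanged and power is 0.76 either way. This holds even if T1, the session that sets the seizure threshold, has systematically lower power.

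**Incomplete sets.** With equal power per session, a patient with k recordings has k/4 of the full total: 75%, 50% or 25% for k = 3, 2 or 1. In SD units of the complete total, a patient at the arm average drops by (1 − k/4)/CV, where CV is the between-patient coefficient of variation of the four-session average. The documents do not give the CV; 20-50% is assumed.

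| Recordings kept | CV 20% | CV 30% | CV 50% |
|---|---|---|---|
| 3 | 1.25 SD | 0.83 SD | 0.50 SD |
| 2 | 2.50 SD | 1.67 SD | 1.00 SD |
| 1 | 3.75 SD | 2.50 SD | 1.50 SD |

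The effect sought is 1.19 SD, so a few such patients per arm matter.

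**Power for Hypothesis 1.1, by simulation.** Assumed: 13 per arm, 2 withdrawals per arm each leaving one to three recordings with equal probability, d = 1.19, untransformed power, within-patient correlation 0.5-0.9.

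| Analysis | CV 20% | CV 30% | CV 50% |
|---|---|---|---|
| Sum of available recordings | 0.42 | 0.59-0.60 | 0.71-0.72 |
| Withdrawn patients excluded (11 per arm) | 0.76 | 0.76 | 0.76 |
| Per-session mean or mixed model | 0.81-0.83 | 0.81-0.83 | 0.81-0.83 |

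- If all four withdraw only after T3, the sum gives about 0.73-0.81. The loss is then small, and at the higher CVs the sum does no worse than exclusion.
- If T1 power is lower by 1.19 SD, the sum gives 0.40-0.73 and a session-adjusted mixed model 0.81-0.84.
- With no true difference and two withdrawals per arm, the sum rejects in 1.1-3.8% of trials, so it is conservative. In the extreme case of all four withdrawals in one arm it rejects in 25%, 17% and 11% at CV 20%, 30% and 50%; the mixed model stays at 5-6%.

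**Hypothesis 1.3.** Section 3 makes T3 the midpoint, and Section 12 ties T3 to the sixth treatment. On that reading only T4 can follow a placement change. If the T2 label in Section 12 is meant literally, T3 can too. Assumed for the simulation: n = 22, a Pearson test (the plan names none), true r = 0.5, within-patient correlation 0.7, 20-40% changing placement after T3, and a change that raises ictal power by 0.5-1.0 SD.

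- Change has no effect on ictal power: the sum detects the association in 0.64 of trials and is unbiased.
- Change raises power but does not improve outcome: detection with the sum is 0.42-0.58. With no true association, wrong-sign significant results are 3-8% (nominal 2.5%).
- Change raises power and changed patients gain about 1 SD of improvement: the sum detects 0.47-0.54, against 0.45-0.51 using pre-change T2-T3 only. Wrong-sign results with no true association are 2.6-3.3%.

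The ranking of the two exposures therefore reverses with an input that the documents do not give.

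**The case against.** The strongest reply on Hypothesis 1.1 is that Section 5 already removes the lost patients. If the analyst does the same, power is 0.76, exactly as with complete data. That is right, and a reader who infers that Sections 5 and 15 contradict each other goes too far: one is a planning allowance, the other a consent provision on keeping data. But Section 15 does contemplate use of those data in the analysis, and Section 13 does not say how a total is formed from them. It is also fair that most of the step from 0.76 to 0.81-0.83 reflects 26 patients instead of 22. The gain specific to dropping the sum is that partial records then help instead of hurting.

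On Hypothesis 1.3, a reader might infer that post-change recordings invalidate the sum and that pre-change power should replace it. The documents do not support that. Power across the treatment actually received is a defensible exposure for a marker of treatment adequacy, and pre-change power would be paired with an outcome that includes post-change treatment. This is a choice of estimand.

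Three other inferences should be resisted.

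- The 50% cap-refusal figure in Section 14 is a termination trigger counted in patients. It gives no per-session missing rate.
- A series ending at treatment six makes T3 and T4 the same session. That lowers the total only if the session is counted once, which the plan does not say.
- If the sum runs over epochs within a session, the total grows with seizure length, which Section 1 says is shorter with methohexital. That is what a total would measure, so it is a reason to state the definition, not a defect.

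**Conclusion.** The point stands for Hypothesis 1.1 as a cheap and worthwhile change to the analysis. As written, the outcome depends on the number of recordings, and the plan leaves a route by which incomplete sets enter. The cost is power: about 0.42-0.72, against 0.76 with exclusion and 0.81-0.83 with a per-session analysis. It shrinks to little or nothing if withdrawals come only after T3. These figures rest on the assumed CV, within-patient correlation and withdrawal pattern. A reader might infer that the between-arm estimate is biased; that requires missingness that differs by arm, which nothing in the documents predicts. The stated sample size is not affected.

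For Hypothesis 1.3 the point is a caveat. T4 can follow a response-driven placement change on either reading of the midpoint, and T3 on one of them. Direction and size depend on what the change does to ictal power and to outcome, and the documents give neither.

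**What to change.** 1. **Hypothesis 1.1.** Define ictal power per session as mean power per epoch, with seizure duration reported separately. Compare arms with a linear mixed model: arm, session, random patient intercept, small-sample degrees of freedom. Use all available recordings, including those that withdrawn participants allow. The session term matters because a plain average over unequal sets of sessions picks up any drift in power over the series.
2. **Withdrawn participants.** Say in Section 13 how their recordings are used, so that Sections 5 and 15 are read together.
3. **Hypothesis 1.3.** Keep the all-session measure as the main exposure. Add a sensitivity analysis restricted to recordings before any placement change.
4. **Wording.** Reconcile the midpoint label in Section 12 (T2) with Section 3 (T3), so that it is clear which recordings can follow a change. State whether the sum runs over sessions or over epochs within a session.

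The cost is slightly more analysis work. No additional patients, visits or recordings are needed.
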